1.0 Objectives

To prolong the time to recurrence for patients with clinical stage I and II uterine LMS assigned to letrozole therapy. The primary endpoint of this study will be a prolongation of time to disease recurrence.

2.0 Background

Letrozole (4,4'-(1H-1,2,4-Triazol-1-ylmethylene)bis-benzonitrile) is a synthetic achiral benzydryltriazole derivative. It is an orally active highly selective non-steroidal competitive inhibitor of the aromatase enzyme system [1,2]. Aromatase inhibitors block the aromatase enzyme, consequently lowering estrogen levels and thereby deprive the tumor of its growth stimulus. Letrozole effectively inhibits the conversion of androgens to estrogens in both *in vitro* and *in* vivo [1]. This property makes it in particular suitable for postmenopausal women whose main source of estrogen is via peripheral aromatization of androgen precursors.

Letrozole is up to 150-250 times more potent than the first generation aromatase inhibitor Aminoglutethimide (AG), *in vitro* and more than 10,000 times as potent as AG in inhibiting aromatase *in* vivo [3]. The high potency of letrozole is not accompanied by any significant effect on adrenal steroidogenesis *in vitro* or *in vivo* over its maximally effective dose range [1,4]. Inhibition of adrenal steroidogenesis resulting in adrenal hypertrophy does occur with therapeutic doses of AG. The high potency and selectivity of letrozole explains its pharmacological profile and high therapeutic index. In postmenopausal patients with advanced breast cancer, daily doses of 0.1 to 5 mg letrozole suppressed plasma levels of estradiol, estrone and estrone sulfate to 75-95% from baseline [1,5]. A Phase III global, multicenter, randomized clinical trial evaluated Letrozole (2.5 mg/day) as a first line hormonal therapy as compared to the present standard of treatment, tamoxifen (20 mg once daily) [6]. This trial accrued 907 postmenopausal women with ER and/or PR positive or unknown receptor breast cancer and locally advanced disease, metastatic disease, or loco-regional recurrence not amenable to treatment by surgery or radiotherapy. Patients received treatment until disease progression or discontinuation for any other reason.

The primary endpoint was time to progression. letrozole was superior to tamoxifen in TTP, reducing the risk of progression by 28% (hazard ratio 0.72, p < .0001). The median TTP was prolonged by 57%, from 6.0 months for tamoxifen to 9.4 months for letrozole The secondary endpoints included overall tumor response rate, clinical benefit, and time to treatment failure. Overall tumor response rate (complete and partial response) was significantly higher with letrozole (32 % vs 21%, p= .0002, irrespective of dominant site of disease. Clinical benefit (CR, PR or stabilization of disease lasting at least 24 weeks was 50% for letrozole vs 38% tamoxifen, p=. 0004. Time to treatment failure was significantly better for letrozole 9.0 months vs 5.7 months for tamoxifen, p =. 0001.

The median overall survival was slightly prolonged for letrozole 34 versus 30 months for tamoxifen. This difference is not significant. However, the study design included a crossover to the other treatment arm at the discretion of the investigator. An analysis was done in the patients

who did not crossover, which demonstrated a 15-month survival advantage in the letrozole treatment group [7]. The data cutoff for this analysis was September 2001, when median follow-up was 32 months, with a maximum observation period of 57 months [6].

Tolerability was similar in both arms of the trial, with 2% of patients on letrozole and 3% of patients on tamoxifen discontinuing core therapy due to adverse events. In conclusion, letrozole has a highly favorable toxicity profile and is superior in TTP and CR compared to tamoxifen in patients with locally advanced and metastatic breast cancer. Based on this study and other supportive data, FDA approved letrozole for first-line hormonal therapy in locally advanced or metastatic breast cancer in January 2001.

A recently completed randomized, double-blind, multicenter study compared the efficacy of 4 months of therapy with letrozole 2.5 mg daily and tamoxifen 20 mg daily as primary treatment in the neoadjuvant setting [8]. The response rate, assessed by clinical palpation (primary endpoint), was 55% for letrozole compared to 36% for tamoxifen (p<0.001). Response rates were similarly significant in favor of letrozole when assessed by ultrasound or mammography.

A double-blind crossover study was conducted in 12 estrogen receptor-postive postmenopausal metastatic breast cancer patients to compare the effects of letrozole and anastrozole on total-body aromatization and plasma estrogen levels. Each regimen was administered for 6 weeks. The data revealed that letrozole suppresses plasma estrogen levels more completely than anastrozole [9]. Letrozole was statistically superior to anastrozole in reducing plasma levels of both estrone sulfate (p=0.019) and estrone (p=0.0037). Patients switching from 6 weeks of anastrozole to 6 weeks of letrozole consistently achieved further estrogen suppression. Conversely, patients switching from 6 weeks of letrozole to 6 weeks of anastrozole experienced an increase in estrogen plasma levels.

A multicenter, double-blind study randomized over 8,000 postmenopausal women with resected, receptor-positive early breast cancer to one of the following arms:

- A. Tamoxifen for 5 years
- B. Femara for 5 years
- C. Tamoxifen for 2 years followed by Femara for 3 years
- D. Femara for 2 years followed by Tamoxifen for 3 years

Of 8,010 women with evaluable data, 4,003 were in the letrozole group and 4,007 in the tamoxifen group. After a median follow-up of 25.8 months, there were 351 events of recurrence, locally or at distant sites, in the letrozole group, and 428 events in the tamoxifen group. Five-year disease-free survival estimates were 84.0% and 81.4%, respectively. [25]

Compared with tamoxifen, letrozole reduced the risk for an event ending a period of disease-free survival (hazard ratio [HR], 0.81; 95% confidence interval [CI], 0.70 - 0.93; P = .003). This reduction especially applied to the risk for distant recurrence (HR, 0.73; 95% CI, 0.60 - 0.88; P = .001).

Adverse events have been analyzed irrespective of whether a symptom was present or

absent at baseline. Most adverse events reported (82%) were Grade 1 and Grade 2 applying the Common Toxicity Criteria Version 2.0.

When considering all grades, a higher incidence of events were seen for Femara regarding fractures (5.7% vs 4%), myocardial infarctions (0.6% vs 0.4%), and arthralgia (21.2% vs 13.5%) (Femara vs tamoxifen respectively). A higher incidence was seen for tamoxifen regarding thromboembolic events (1.2% vs 2.8%), endometrial cancer (0.2% vs 0.4%), endometrial proliferative disorders (0.3% vs 1.8%) Femara vs tamoxifen respectively.

In the adjuvant setting, an increase in total cholesterol (generally non-fasting) in patients who had baseline values of total serum cholesterol within normal range, and then subsequently had an increase in total serum cholesterol of 1.5 ULN was 173/3203 (5.4%) on letrozole vs 40/3224 (1.2%) on tamoxifen. Lipid lowering drugs were used by 18% of patients on letrozole and 12% on tamoxifen.

Uterine leiomyosarcomas (LMS) are rare, accounting for less than five percent of all malignant uterine neoplasms. Approximately 85% of women present with clinical stage I or II disease (i.e., disease limited to disease that is limited to the uterus and cervix). Lymph node metastasis is not common for patients with LMS, therefore, clinical staging is adequate and surgical re-exploration is not necessary for patients who are not initially staged [10]. Despite the low incidence of high stage disease, approximately 50% of patients will recur within two years [10-12]. Most of these patients recur outside of the pelvis. The Gynecologic Oncology Group evaluated the role of adjuvant radiation therapy in patients (n=48) with clinical stage I and II disease [11]. There was no difference in the progression-free interval, absolute two-year survival rate, or site of first recurrence between patients who received pelvic radiation (n=11) and those that did not (n=37). This is not surprising since most recurrences were outside of the pelvis (83%). 48% of the patients recurred and most of these patients recurred within 17 months of diagnosis. Adjuvant chemotherapy was also evaluated for patients who did not receive chemotherapy. This difference was not statistically significant.

Several studies have evaluated the rate of hormone receptor expression in patients with LMS of the uterus [13-21]. 40-87% of leiomyosarcomas express the estrogen receptor (ER) and 38-80% express the progesterone receptor (PR). Because of this high expression, estrogen may act as a growth factor that stimulates cell proliferation and tumor growth.

Hormonal manipulation is commonly used to control the growth of benign leiomyomas. Given the relatively high rate of hormone receptor positivity for LMS, we hypothesize that by decreasing systemic estrogen using an aromatase inhibitor, we may be able to prolong the time to recurrence for patients with this disease. [26-28]

3.0 Treatment Plan

3.1. Overall study design

This is a randomized phase II study of Femara (letrozole) administered orally on a daily basis to patients with newly diagnosed clinical stage I and II LMS. Using an adaptive randomization,

patients will be assigned to either the treatment arm (letrozole group) or observation. The primary outcome for this trial is the time to progression or death.

3.3. Study population

3.3.1. Patient population

Patient enrollment will be open to any individual with clinical stage I and II uterine LMS seen in the Gynecologic Oncology Center at M. D. Anderson Cancer Center. Hormone receptor positivity is an eligibility requirement.

3.3.2. Inclusion and exclusion criteria

Inclusion criteria

To be eligible for the study, patients must fulfill all of the following criteria:

- 1. Patients must have signed an approved informed consent.
- 2. Histologically confirmed uterine leiomyosarcoma with disease limited to the uterus (determined by surgical staging or radiologic imaging).
- 3. Tumors must express ER positivity by immunohistochemistry (ER expression >10% by immunohistochemistry).
- 4. Patients must have a hysterectomy and bilateral oophorectomy prior to initiation of therapy.
- 5. All patients must have no measurable disease. Measurable disease is defined as lesions that can be measured by physical examination or by means of imaging techniques. Imaging must be done within 6 weeks of study entry.
- 6. Patients must have a Zubrod performance status of 0, 1, or 2.
- 7. Patients must have a pretreatment granulocyte count (i.e., segmented neutrophils + bands) of >1,000/Fl, a hemoglobin level of ≥9.0 gm/dL and a platelet count of >75,000/dL.
- 8. Patients must have an adequate renal function as documented by serum creatinine ≤2.0 mg/dL.
- 9. Patients must have adequate hepatic function as documented by a serum bilirubin 2.5 mg/dL.
- 10. Aspartate transaminase (SGOT) must be $\leq 3x$ institutional upper limit of normal.
- 11. Patients must have recovered from the effects of prior surgery.
- 12. No more than 12 weeks must have elapsed from hysterectomy.
- 13. Patients must be 18 years of age or older.

Exclusion criteria

Patients meeting any of the following criteria are ineligible to participate in this study:

- 1. Patients who do not have pure uterine sarcomas (i.e., no mixed malignant mullerian tumors).
- 2. Patients with any other severe concurrent disease, which would make the patient inappropriate for entry into this study, including significant hepatic, renal, or gastrointestinal diseases.
- 3. Patients with a history of prior malignancy except for adequately treated basal cell or squamous cell skin cancer, in situ cervical cancer, or other cancer for

which the patient has been disease-free for at least five years.

- 4. Patients who were taking or have a history of taking letrozole or any other aromatase inhibitor.
- 5. Patients with active or uncontrolled systemic infection.
- 6. Patients with history of uncontrolled cardiac disease; i.e., uncontrolled hypertension, unstable angina, recent myocardial infarction (within prior 6 months), uncontrolled congestive heart failure, and cardiomyopathy with an ejection fraction under 40%.
- 7. Patients who are pregnant or breast-feeding.
- 8. Presence of clinically apparent untreated central nervous system metastases
- 9. Presence of carcinomatous meningitis.
- 10. Patients currently receiving chemotherapy or radiation therapy.

MDACC will not exclude any potential subject from participating in this or any study solely on the basis of ethnic origin or socioeconomic status. Every attempt will be made to enter all eligible patients into this protocol and therefore address the study objectives in a patient population representative of the MDACC cancer population.

3.3.3. Interruption or discontinuation of treatment

A genuine effort must be made to determine the reason(s) why a patient fails to return for the necessary visits or is discontinued from the trial. Information regarding the reason for not completing the trial will be recorded in the patient's medical record.

Reasons that a patient may discontinue participation in this clinical study include:

- 1. adverse event(s)
- 2. abnormal laboratory value(s)
- 3. abnormal test procedure result(s)
- 4. unsatisfactory therapeutic effect
- 5. subject's condition no longer requires study drug
- 6. protocol violation
- 7. subject withdrew consent
- 8. lost to follow-up
- 9. death.

Any patient who receives at least one dose of trial medication will be included in the safety analysis.

3.4. Drug Information

Description:

Letrozole is used to treat certain types of breast cancer in women. Female hormones that occur naturally in the body can increase the growth of some cancers. Letrozole works by decreasing the amounts of these hormones in the body. The medicine is meant to be used

only by women who have already stopped menstruation.

The most commonly used brand name is Femara. The chemical name is 4,4'-(1H-1,2,4-Triazol-1-ylmethylene)dibenzonitrile.

Drug Supply: Letrozole will be supplied by Norvartis Pharmaceuticals.

Availability and storage: Available as 2.5 mg tablet or oral administration. Should be stored at room temperature.

Dosage: 2.5mg tablet PO daily

Pharmacokinetics: Letrozole is rapidly and completely absorbed from the gastrointestinal tract. The terminal elimination half-life is about two days. Daily doses of 0.1mg to 5 mg Letrozole suppresses plasma concentrations of estrone, and estrone sulfate by 75% to 95% from baseline with maximal suppression achieved within two to three days.

Toxicity: Letrozole is well tolerated by most patients. The common adverse effects reported with daily administration of letrozole include headache, mild nausea, hot flashes, diarrhea, fluid retention and muscle cramps. Other side affects include burning, dryness or itching of the vagina. It may cause vaginal bleeding or discharge.

Letrozole may cause breast pain, chills, fever, flu-like symptoms and mental depression. It may also cause bone pain, joint or muscle pain. It may cause anxiety, confusion, increased thirst and urination, loss of appetite or weight loss. It has also been associated with skin rash, or itching, sleepiness, trouble sleeping, unusual tiredness and weakness. Letrozole sometimes causes a loss of hair. Letrozole may increased risk for blood clots, which could lead to a heart attack or a stroke.

Adverse Effects are usually mild to moderate and rarely necessitate discontinuation of treatment

Treatment compliance

Patients will remain on study until disease progression. For the purposes of this trial the final data collection point is at the time of disease progression. For those patients assigned to the treatment group, records of study medication used and dosages administered will be kept during the study. Drug accountability will be noted during follow-up visits and at the completion of the trial. Patients will be asked to return all unused medication.

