- 6. Zubrod performance status
- Assessment of treatment-related toxicities (study drug arm) using the grading schema in NCI Common Terminology Criteria for Adverse Events, Version 3.0.

Follow-up and further imaging:

Follow-up will be at the discretion of the patient's primary physician and based on physical findings.

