Any Serious Adverse event occurring in a patient after providing informed consent, while receiving study drug, and until four weeks after stopping study drug must be reported by FAX **Sector**) to Novartis Pharmaceuticals CS&E Department within 24 hours of learning of it's occurrence, even if it is not felt to be drug related. It is requested that SAEs are reported to Novartis using the Norvartis SAE form (Appendix E)

Serious adverse events

A serious adverse event is an undesirable sign, symptom or medical condition which:

- 1. is fatal or life-threatening
- 2. required or prolonged hospitalization
- 3. results in persistent or significant disability/incapacity
- 4. constitutes a congenital anomaly or a birth defect
- 5. are medically significant, may jeopardize the subject and may require medical or surgical intervention to prevent one of the outcomes listed above.

Any serious adverse event occurring after the patient has provided informed consent and until 4 weeks after the patient has stopped study participation must be reported.

Grading/Rating Scale

- All adverse events reported during the study will be evaluated and graded on a scale of 1-5. The NCI Common Terminology Criteria for Adverse Events, v3.0 (CTCAE) will be used to determine the grade for all toxicities.
- 2. For any adverse events, which are not listed in the CTCAE the following rating system, will be used:

Grade Description

- 0 No AE or within normal limits
- 1 Mild AE (minor; no specific medical intervention; asymptomatic laboratory findings only, radiographic findings only; marginal clinical relevance)
- 2 Moderate AE (minimal intervention; local intervention; noninvasive intervention [packing, cautery])
- 3 Severe and undesirable AE (significant symptoms requiring hospitalization or invasive intervention; transfusion; elective interventional radiological procedure; therapeutic endoscopy or operation)
- 4 Life-threatening or disabling AE (complicated by acute, life-threatening metabolic or cardiovascular complications such as circulatory failure, hemorrhage, sepsis. Life-threatening physiologic consequences; need for intensive care or emergent invasive procedure; emergent interventional radiological procedure, therapeutic endoscopy or operation)
- 5 Fatal AE

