3.6 Efficacy Assessment

Patients receiving letrozole will continue until progression or drug related toxicity. Those assigned to the observation group will be followed until disease progression. Progression will be defined as appearance of one or more new lesions on clinical exam or on radiologic imaging. At the physician's discretion, clinical findings can warrant further radiologic imaging. If the imaging reveals a new lesion, recurrent disease should be biopsy proven.

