6.0 Statistical Design

We will accrue a minimum of 10 patients and a maximum of 80 patients at a rate of 2 patients per month. The primary outcome for this trial is the time to progression or death. Patients treated with standard of care (observation) have median progression-free survival (PFS) of 24 months [10]. We will follow all patients for at least 24 months following treatment.

Patients will be randomized between observation and letrozole using a Bayesian adaptive algorithm [22]. Details of this methodology are given in the "Technical Details" section below. The first 10 patients will be randomized fairly between the 2 treatment arms. After 10 patients are enrolled there will be 5 patients on each treatment arm. As the trial progresses and data accrue the randomization will become unbalanced in favor of the treatment that, on average, has better results in terms of PFS, so that each successive patient is more likely to receive the treatment showing better results.

The trial will be stopped early and a treatment selected as being "better" if the probability is 0.90 or more that one treatment's PFS is longer than the other treatment's PFS. However, if all 80 patients are enrolled, then a treatment will be selected as being "better" if the probability is 0.80 or more that one treatment's PFS is longer than the other treatment's PFS.

The operating characteristics of this study design are summarized in Table 1. These operating characteristics are based on 1000 simulations of the study design for 6 possible scenarios.

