6.1.2 Secondary Outcome

We will estimate the overall survival (OS) with the Kaplan-Meier product-limit estimator for each arm, and we will compare the OS between the 2 arms with the log-rank test. We will model OS with the Cox proportional hazards regression model to estimate the hazard ratio for treatment (letrozole : observation), and we will construct a 95% confidence interval for this hazard ratio.

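### Overall survival analyses are planned, but the protocol gives conflicting rules on whether patients are followed after progression

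*Combined protocol and SAP*

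**What the plan says.** Five places bear on follow-up after progression.

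- **Section 6.1.2** commits to a survival analysis: "We will estimate the overall survival (OS) with the Kaplan-Meier product-limit estimator for each arm". A log-rank test between the arms and a Cox hazard ratio with a 95% confidence interval follow.
- **Section 3.4 (Drug Information, under Treatment compliance):** "Patients will remain on study until disease progression". The next sentence is: "For the purposes of this trial the final data collection point is at the time of disease progression".
- **Section 3.6 (Efficacy Assessment):** "Those assigned to the observation group will be followed until disease progression".
- **Section 6.0 (Statistical Design):** "We will follow all patients for at least 24 months following treatment".
- **Section 3.5.2 (Follow-up and further imaging):** "Follow-up will be at the discretion of the patient's primary physician and based on physical findings".

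The only other data capture beyond progression is in section 3.5.3, where serious adverse events "until 4 weeks after the patient has stopped study participation must be reported". Section 1.0 does not list OS among the objectives.

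**The concern.** These statements cannot all hold. A patient who progresses at month 6 has reached the end of data collection under section 3.4 but is still to be followed under section 6.0. In the observation arm, the 24 months of section 6.0 have no stated start, because there is no treatment to count from. No section says which rule governs. The visit schedule in the supplied text has no survival contact, and section 6.1.2 gives no OS censoring rule.

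Most deaths in this disease would be expected after recurrence. If vital status stops at progression, patients leave the OS risk set just when their risk of death rises. That is informative censoring, and it pushes the Kaplan-Meier curve upward. If follow-up stops at progression in one arm only, the comparison between arms is distorted as well.

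**Working it through.** The documents give no OS rate, event count or power, so there is no OS figure of theirs to reproduce. The calculation below shows how far the result depends on which section governs.

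**Inputs from section 6.0:** 80 patients at 2 per month, so accrual lasts 80/2 = 40 months; observation median PFS 24 months.

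**Assumptions, not in the documents:**
- full accrual, exponential times, no treatment effect, 1:1 allocation;
- data cut at month 64 (40 + 24), which is one reading of section 6.0;
- death without progression at d = 0, 1, 3 or 5% per year, held within the 24-month PFS median;
- median survival after progression 6, 12 or 24 months.

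**Formulas**
- PFS hazard λ = ln 2/24 = 0.02888 per month. The share of PFS events that are deaths is q = (d/12)/λ, which at 5% is 0.004167/0.02888 = 0.144.
- Chance of a PFS event by the cut: P = 1 − [exp(−24λ) − exp(−64λ)]/(40λ) = 1 − (0.5 − 0.1575)/1.155 = 0.7035.
- True OS, with μ = ln 2/(median survival after progression): S(t) = exp(−λt) + (1 − q)λ[exp(−μt) − exp(−λt)]/(λ − μ). When μ = λ, the second term is (1 − q)λt·exp(−λt).

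**True 36-month OS**
- Highest (d = 0, 24 months): 0.3536 × (1 + 1.040) = 0.72.
- Lowest (d = 5%, 6 months): 0.3536 + 0.856 × 0.02888 × (0.0156 − 0.3536)/(0.02888 − 0.1155) = 0.45.

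**Section 3.4 taken literally.** Captured deaths are 80 × q × P, from 0 up to 80 × 0.144 × 0.7035 = 8.1. With censoring at progression, Kaplan-Meier estimates exp(−d × 3) at 36 months, from 1.00 down to exp(−0.15) = 0.86.

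**Section 6.0 as 24 months from entry** (follow-up to the later of progression or month 24). Captured deaths are 80 × [1 − S(24)] + 80 × q × (P − 0.5). The high end is 80 × 0.375 + 80 × 0.144 × 0.2035 = 32. The low end is 80 × (1 − 0.847) = 12.

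Ranges over the 12 combinations of d and post-progression survival, by simulation with 400,000 patients per combination, scaled to 80:

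| Reading | Deaths captured | 36-month OS |
|---|---|---|
| Vital status to the cut, both arms | 29 to 50 | 0.45 to 0.72 (true) |
| Section 3.4 literal | 0 to 8 | 0.86 to 1.00 |
| Section 3.4 plus the 4-week SAE window | 1.5 to 13 | 0.79 to 0.97 |
| Section 6.0 as 24 months from entry | 12 to 32 | too high by 0.09 to 0.18 (24-month OS correct) |
| Section 6.0 as 24 months after progression, both arms | 24 to 49 | too high by about 0.01 |

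The last reading drifts later on. In a companion calculation with 2 to 10% of PFS events being deaths and post-progression medians of 12 to 24 months, its 48-month OS was up to about 0.04 too high (for example 0.565 against 0.524).

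**Precision.** The standard error of the log hazard ratio is about 2/√deaths. It is 0.28 to 0.37 with 50 to 29 deaths, and 0.70 (2/√8.1) at best under section 3.4 literal.

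**Mixed reading:** section 6.0 for letrozole (24 months after treatment stops at progression) and section 3.6 for observation. Expected progression-free follow-up is P/λ = 0.7035/0.02888 = 24.4 months per patient in each arm.
- *d = 5%, post-progression median 24 months.* Observation: 0.1015 deaths per 24.4 months. Letrozole: 0.354 deaths, of which 0.252 follow progression over 0.252/0.02888 = 8.7 months. The rate ratio is (0.354/33.1)/(0.1015/24.4) = 2.6.
- *d = 1%, post-progression median 6 months.* Letrozole: 0.595 deaths, of which 0.575 follow progression over 0.575/0.1155 = 5.0 months. The ratio is (0.595/29.3)/(0.0203/24.4) = about 24.
- *d = 0.* The observation arm has no captured death, and the ratio cannot be estimated.

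The true ratio is 1 throughout.

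**The case against.** The strongest reply is that the section 3.4 sentence sits under Treatment compliance and may concern drug records only, while the statistical section promises follow-up of all patients. That reading is possible. Against it, the sentence speaks of the trial as a whole, the one before it keeps all patients on study only until progression, and section 3.6 repeats that end point for the untreated arm under efficacy. Section 6.0 does not say that it overrides either, and it gives no contact method or interval.

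Fatal serious adverse events within four weeks of leaving the study are reportable, so some deaths soon after progression would be known. This stands, and it raises the floor only to about 1.5 to 13 deaths.

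The absence of survival contact is established only for the text reviewed. Consent pages, appendices and some other pages were not available, and section 3.2 does not appear in it.

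The illustration has limits. It ignores adaptive allocation and early stopping, and a smaller trial would have fewer deaths under every reading.

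Two stronger readings are tempting. A reader might infer that OS will certainly be censored at progression. The documents do not establish this, because section 6.0 can be read in a way that leaves OS nearly unbiased. A reader might also infer that the primary result is compromised. PFS as defined is complete at progression or death, and neither the randomisation probabilities nor the stopping rules use OS. How patients who stop letrozole for toxicity are followed up to progression is a separate question.

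**Conclusion.** The inconsistency is real and should be fixed. Sections 3.4, 3.6, 6.0 and 6.1.2 do not describe one follow-up rule, and the OS result depends heavily on which is followed. Under the stated assumptions it runs from nearly unbiased at 36 months to an estimate built almost only on deaths without progression. If the two arms are followed differently, it becomes a spurious rate ratio of about 2.6 to 24 against letrozole where death without progression is 1 to 5% per year. The sizes rest on assumed death rates; the direction of the bias requires only that progression raises the risk of death. Because OS is secondary and drives no design decision, this is a correction to make and not a flaw that undermines the trial.

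**What to change.** Reconcile sections 3.4, 3.5.2, 3.6, 6.0 and 6.1.2 in one amendment:

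- **Section 3.4:** limit the end-of-data-collection sentence to PFS and treatment data.
- **Sections 3.5.2 and 3.6:** state that vital status is collected after progression or end of treatment, by the same method and schedule in both arms (chart review or telephone, at an interval the sponsor chooses), until the analysis cut-off.
- **Section 6.0:** define the start of the 24 months identically in both arms, for example at randomisation.
- **Section 6.1.2:** define OS as the time from randomisation to death from any cause, with patients not known to have died censored at the date last known alive and not at progression.

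If the sponsor does not want this follow-up, the alternative is to drop the OS comparison.

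The cost is an amendment, which sections 4.0 and 7.1.1 route through the company and the IRB, and a small amount of chart or telephone work on at most 80 patients. No visits or scans are added.
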